1 SYNOPSIS

Title: A Multicenter, Long-Term, Rollover Extension Study of Rovalpituzumab Tesirine						
Background and Rationale:	The purpose of this extension study is to provide ongoing safety and efficacy follow-up of subjects who are participating in a rovalpituzumab tesirine study that has completed the primary analysis and is closing.					
Objective and Study Endpoints:	The objective of this study is to provide long-term follow-up for subjects remaining on a rovalpituzumab tesirine study that has completed the primary analysis and is closing. Safety and limited efficacy data on patients retreated with rovalpituzumab tesirine will be collected. There is no formal statistical analysis of safety or efficacy data in this study.					
Investigators:	Multicenter					
Study Sites:	This extension study will be conducted in ~20 sites in the same countries as the rovalpituzumab tesirine parent studies; including but not limited to, Canada, France, Latvia, Spain, the United Kingdom, and the United States. More study sites and countries may be included as other rovalpituzumab tesirine parent studies complete their primary analyses and close.					
Study Population and Number of Subjects to be Enrolled:	Study population includes subjects who were enrolled in rovalpituzumab tesirine treatment studies, but have not yet reached 1 or more endpoints in the parent study at the time of primary analyses. In addition, subjects who were eligible for retreatment based on the criteria written in the parent study will have the option of retreatment in this study.					
Investigational Plan:	This is a phase 2 multicenter, long-term, rollover follow-up extension study. The schedule of assessments will depend on whether subjects enter the study in post-treatment follow-up or are receiving ongoing rovalpituzumab tesirine treatment from the parent study. This extension study includes 2 Study Arms: • Arm A: Subjects who enter the extension study while in post-treatment follow-up. This arm includes optional rovalpituzumab tesirine retreatment for those who qualify, based on retreatment criteria written in the parent protocol. Most subjects from all studies will be in this arm. • Arm B: Subjects who enter the extension study while receiving ongoing rovalpituzumab tesirine treatment (e.g., Study SCRX001-007)					

Key Eligibility Criteria:

For both Arms A and B; eligibility criteria are that a subject have enrolled, participated in, and received at least 1 dose of rovalpituzumab tesirine in a parent study.

Additional eligibility criterion for Arm A is that subjects who discontinued the study drug in the parent study have completed the treatment emergent AE reporting window (e.g., 30 days post last dose for Study SCRX001-002).

For subjects who elect optional retreatment in Arm A, below are key eligibility criteria:

- Tolerated their initial 2 doses of rovalpituzumab tesirine
- Achieved clinical benefit from rovalpituzumab tesirine, defined as stable disease or better, and is determined that the subject would potentially benefit from additional treatment

 OR
- Achieved clinical benefit as defined by stable disease or better and experienced radiographic disease progression at least 12 weeks after last dose of rovalpituzumab tesirine per RECIST 1.1
- Received no other systemic anti-cancer therapy after rovalpituzumab tesirine
- Laboratory values meeting the following criteria:
- Absolute neutrophil count (ANC) ≥ 1,500/µL;
- Platelet count ≥ 75,000/μL;
- Hemoglobin ≥ 8.0 g/dL;
- Serum total bilirubin ≤ 1.5 × upper limit of normal (ULN) or ≤ 3 × ULN for subjects with Gilbert's disease;
- Serum alanine aminotransferase (ALT) and aspartate aminotransferase (AST) ≤ 2.5 × ULN (≤ 5 × ULN if evidence of hepatic involvement by malignant disease);
- Serum creatinine ≤ 1.5 × ULN or estimated glomerular filtration rate (eGFR) ≥ 30 mL/min/1.73 m² as calculated by the 4-variable Modification of Diet in Renal Disease study equation (GFR (mL/min/1.73 m²) = 175 × (serum creatinine [mg/dL])-1.154 × (age [years])-0.203 × 0.742 (if female) × 1.212 (if African American).
- Recovery to Grade 1 or baseline of any clinically significant rovalpituzumab tesirine related toxicity (excluding alopecia) prior to initiation of study drug
- In subjects with central nervous system (CNS) metastases, documentation of stable or improved status based on brain imaging for at least 2 weeks after completion of definitive treatment and within 2 weeks prior to initiation of retreatment, off or on a stable dose of corticosteroids. (Note: Definitive treatment may include surgical resection, whole brain irradiation, and/or stereotactic radiation therapy.)

Study Drug and Duration of Treatment:	For subjects receiving study drug in this study, rovalpituzumab tesirine (0.3 mg/kg or previously adjusted dose) will be administered as follows:
	 Arm A (Optional Retreatment): IV once every 6 weeks beginning on Day 1 (day of dosing) for 2 dose (cycles) per subject per retreatment period.
	 Arm B: IV once every 6 weeks beginning on Day 1 (day of dosing). Subjects will receive rovalpituzumab tesirine on Day 1 of each 6-week cycle, omitting every third cycle until disease progression or study drug discontinuation.
	 Oral dexamethasone 8 mg (or alternative corticosteroid at equivalent dosing) will be administered twice daily on Day -1, Day 1, and Day 2 for all subjects receiving rovalpituzumab tesirine.
Date of Protocol Synopsis:	20 May 2019

2 INTRODUCTION

2.1 Background and Rationale

Why Is This Study Being Conducted

Rovalpituzumab tesirine is an antibody-drug conjugate (ADC) that targets delta-like protein 3 (DLL3), which is uniquely expressed on the cell surface of neuroendocrine tumor cells, including small cell lung carcinoma (SCLC). It is being developed for the treatment of DLL3-expressing SCLC and being explored for the treatment of other DLL3-expressing solid tumors.

The purpose of this extension study is to provide ongoing safety and efficacy follow-up of subjects who are participating in a rovalpituzumab tesirine study that have completed their primary analyses and are closing and to provide optional retreatment for those who qualify.

Clinical Hypothesis

No clinical hypothesis is being tested.

2.2 Benefits and Risks to Subjects

As of 30 June 2018, a total of 1246 subjects have received study medication in rovalpituzumab tesirine clinical trials.

It is possible that some subjects may not benefit from Rova-T treatment. Subjects with relapsed/recurrent SCLC enrolled in the TAHOE Study "A Randomized, Open-Label, Multicenter, Phase 3 Study of Rovalpituzumab Tesirine Compared with Topotecan for Subjects with Advanced or Metastatic DLL3^{high} SCLC who have First Disease Progression During or Following Front-Line Platinum-Based Chemotherapy" had shorter survival in the Rova-T arm compared with the topotecan control arm.

Other preliminary safety and efficacy data from ongoing studies support further development of rovalpituzumab tesirine for subjects with relapsed/refractory DLL3-expressing SCLC and further exploration in other DLL3-expressing solid tumors. For further details, refer to the Rovalpituzumab Tesirine Investigator Brochure.¹

3 STUDY OBJECTIVES AND ENDPOINTS

3.1 Objectives

The objective is to provide long-term follow-up for subjects remaining on a rovalpituzumab tesirine study that has completed the primary analysis and is closing. Safety and limited efficacy data on patients retreated with rovalpituzumab tesirine will be collected.

3.2 Efficacy Evaluations

[figure not shown]
There are no efficacy objectives and endpoints for this extension study. Limited efficacy data will be collected and listed. Aggregate summaries and other statistical analyses of efficacy data are not planned. Efficacy data including radiographic disease response assessment by Response Evaluation Criteria in Solid Tumors (RECIST) version 1.1² and survival for each subject will be collected and only raw data/listings will be generated.

For efficacy listing information, refer to Section 7.4.

3.3 Safety Evaluations

Safety evaluations include adverse event monitoring, physical examinations, echocardiography, vital sign measurements, performance status, and clinical laboratory testing. Adverse events (AEs) will be collected from the time of enrollment until the end of the study. For subjects receiving treatment/retreatment in this study, all AEs regardless of seriousness or causality, will be reported through 70 days after the last dose of treatment. Only treatment-related serious adverse events (SAEs) will be collected post 70 days of the last dose of rovalpituzumab tesirine received in the study. In those subjects in Arm A who are not receiving treatment, only treatment-related SAEs will be collected. The AE reporting windows are described below in the schema.

Adverse Event Reporting

Last rovalpituzumab tesirine dose refers to the last dose received by the subject in either the parent study (Arm A, No Retreatment) or this extension study (Arm A Retreatment or Arm B).

Further details on AE reporting are provided in Section 6.1 and the Operations Manual, Section 4. For statistical analysis provided for study disclosure, refer to Section 7.5.

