7.5 Statistical Analyses for Safety

Adverse events will be coded and summarized by system organ class and preferred term (and severity) according to the Medical Dictionary for Regulatory Activities (MedDRA) version 20.1 or higher. Clinical toxicity grades modified from the NCI CTCAE version 4.0 will be used in the grading of AEs and laboratory abnormalities that are reported as AEs.

No safety analyses will be performed. A listing of data for subjects experiencing AEs will be provided. Laboratory measurements collected on the eCRF will also be listed.

For study disclosure, the following safety data will be summarized:

- For Arm A: Serious adverse events related to treatment will be summarized.
- For Arm B and those who are retreated on Arm A: AEs from enrollment to 70 days after the last dose and SAEs related to rovalpituzumab tesirine from 71 days after the last dose until the end of study will be summarized.

Definitions of AEs are provided in Section 6.1 and the Operations Manual, Section 4.

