- b. Response assessment and brain MRI (if clinically indicated) to be performed only in subjects who have not yet experienced radiographic disease progression.
- NOTES: The End of Treatment (EOT) assessment is conducted at a clinic visit. This visit should occur 42 days ± 3 days after last dose, or within 7 days of documentation of the decision to discontinue treatment, whichever is later.

LONG TERM FOLLOW-UP VISITS: EVERY 6 WEEKS ± 1 WEEK UNTIL 24 WEEKS AFTER FIRST ROVALPITUZUMAB TESIRINE DOSE, THEN EVERY 12 WEEKS ± 1 WEEK (FOR POST-TREATMENT FOLLOW-UP) OR EVERY 12 WEEKS ± 2 WEEKS (FOR SURVIVAL FOLLOW-UP)

□ INTERVIEW^a

- Adverse events
 - Concomitant medications
- Survival status/Death (date and cause)

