ANC < 1,000/μL	 Hold Growth factors are recommended to be used per ASCO/NCCN/institutional guidelines With resolution restart at original dose for next cycle If no resolution, reduce dosing 		
Toxicity on Subsequent Days of Cycle			
Platelets < 25,000/μL for greater than 7 days, OR Thrombocytopenia with bleeding observed in the previous cycle	 Hold With resolution restart at reduced dose per for next cycle If no resolution, discontinue dosing 		
ANC < $500/\mu L$ for greater than 7 days, OR Neutropenic fever (ANC < $1,000/\mu L$ and single temperature > $38.3^{\circ}C$ or temperature > $38.0^{\circ}C$ for more than 1 hour)	 Hold Growth factors are recommended to be used per ASCO/NCCN/institutional guidelines^b With resolution restart at reduced dose per for next cycle If no resolution, discontinue dosing 		

Abbreviations: ANC = absolute neutrophil count; ASCO = American Society of Clinical Oncology; National Comprehensive Cancer Network

- a. The maximum allowed dose interruption is 6 weeks.
- b. Colony stimulating factors include filgrastim or sargramostim.

Special Toxicity Management

Management of Serosal Effusions/Serositis

Serosal effusions (pleural, pericardial), alone or in combination with generalized or peripheral edema and/or hypoalbuminemia, have been observed with rovalpituzumab tesirine. These events have the potential to be life-threatening (e.g., pericardial tamponade), therefore development of any of these events or worsening from baseline warrants prompt evaluation by the investigator or designee.

For serosal effusions considered clinically significant (e.g., grade 2 or higher and considered related to rovalpituzumab tesirine), administration of systemic corticosteroids should be considered (e.g., a tapered regimen of dexamethasone, such as up to 8 mg orally BID for 5 days, followed by 4 mg orally BID for 5 days, then 2 mg orally BID for 5 days). Alternatively, nonsteroidal therapies may be considered, such as non-steroidal anti-inflammatory drugs (e.g., ibuprofen 400 to 600 mg orally 3 to 4 times daily) or colchicine (e.g., 0.6 mg orally 2 to 3 times daily) for 1 to 2 weeks. Symptomatic pleural and pericardial effusions should be drained as appropriate for symptom relief. Effusions can recur/reaccumulate after drainage.

Management of Edema

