6 STUDY DRUG

6.1 Treatments Administered

Rovalpituzumab tesirine and dexamethasone (or alternative) will be administered at the visits listed in Section 2. General study drug information for rovalpituzumab tesirine is presented in Table 3.

Table 3. Investigational Products: Royalpituzumab Tesirine

Investigational Product Name	Rovalpituzumab Tesirine
Route of Administration	IV
Combination Drugs	Not applicable
Formulation	10 mg 15 mg 30 mg
Dosage Form	Powder for solution for infusion in 10 mg, 15 mg, or 30 mg vial (10 mg/mL when reconstituted)
Dose and units	0.3 mg/kg or previously adjusted dose
Drug Preparation	Reconstitution of lyophilized powder with sterile water for injection per EDP
Frequency of administration	Day 1 of every cycle (1 cycle = 42 days/6 weeks); Note: not administered every third cycle in Arm B
Storage Conditions	Stored at refrigerated temperature (2° to 8°C/36° to 46°F), protected from light, and must not be frozen. Specific storage conditions for reconstituted and diluted IP will be provided in a separate document outside of this protocol

Rovalpituzumab Tesirine

Rovalpituzumab tesirine will be supplied as lyophilized drug, as shown in Table 3. Rovalpituzumab tesirine is intended for IV infusion after further dilution in a 50 mL or 100 mL infusion bag (50 mL infusion bag is recommended) containing 0.9% Sodium Chloride Injection, USP, or equivalent, to achieve the desired dose level for administration. Rovalpituzumab tesirine will be infused over 30 minutes (20 - 45 minute infusion window). The rate should be adjusted based on patient tolerability. Further details regarding reconstitution of study drug are provided in the extemporaneous dose preparation (EDP).

Since rovalpituzumab tesirine dosing is based on body weight, multiple vials of reconstituted drug product may be required to achieve the desired dose. Specific dose preparation and documentation details will be provided to the site pharmacy in a separate document.

A complete description of rovalpituzumab tesirine chemistry and formulation may be found in the Investigator's Brochure.

Dexamethasone (or Equivalent Corticosteroid)

Dexamethasone tablets (various formulations) are to be taken orally at a dose of 8 mg BID.

Dexamethasone will be self-administered by subjects on Day -1, Day 1, and Day 2 of each cycle when

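### In Arm B the planned 84-day dosing gap outlasts the 70-day AE window, so some AEs late in an omitted cycle count only if another dose follows

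*Combined protocol and SAP*

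**What the plan says.** **Dosing.** The Synopsis gives the Arm B schedule: "Subjects will receive rovalpituzumab tesirine on Day 1 of each 6-week cycle, omitting every third cycle until disease progression or study drug discontinuation". Operations Manual 6.1 (Table 3) gives the cycle length: "Day 1 of every cycle (1 cycle = 42 days/6 weeks); Note: not administered every third cycle in Arm B". In an omitted cycle the visits and assessments still take place; only study drug and dexamethasone are left out (Operations Manual 2.3).

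**AE window.** For subjects treated in this study, Section 3.3 says that "all AEs regardless of seriousness or causality, will be reported through 70 days after the last dose of treatment". After that, "Only treatment-related serious adverse events (SAEs) will be collected post 70 days of the last dose of rovalpituzumab tesirine received in the study". The anchor is defined in the same section: "Last rovalpituzumab tesirine dose refers to the last dose received by the subject". Section 3.3 also contains a general sentence that has AEs collected from enrollment to study end, with no 70-day limit.

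**Definition and summary.** Operations Manual 4.1 counts an event as treatment-emergent if it starts or worsens between the first dose and 70 days after the last. Section 7.5 builds the disclosure summary for Arm B and for retreated Arm A subjects on the same limit: "AEs from enrollment to 70 days after the last dose and SAEs related to rovalpituzumab tesirine from 71 days after the last dose".

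**Stopping and holding.** On the End of Treatment visit, Operations Manual 2.3 says: "This visit should occur 42 days ± 3 days after last dose, or within 7 days of documentation of the decision to discontinue treatment". The later of the two dates applies. A footnote to the hematologic toxicity table in Operations Manual 4.4 reads: "The maximum allowed dose interruption is 6 weeks".

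**The concern.** The window is anchored to the last dose, which is known only in retrospect. That does no harm while doses are closer together than the window is long. Across an omitted cycle they are not: a subject can still be on study treatment, awaiting the next planned dose, and already be more than 70 days from the previous one.

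For an event in that stretch, inclusion depends on what happens next. If the subject goes on, the later dose moves the anchor and the event is inside the window. If the subject stops, the anchor stays where it was and the event falls outside. Exclusion therefore falls only on subjects who discontinue, including those who discontinue because of the event. A safety summary should not select events on a later outcome in this way.

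The exception for treatment-related SAEs covers only part of this. By the documents' own account most edema is grade 1 or 2 (Operations Manual 4.4) and most skin reactions are grade 2 or lower (Section 6.3). Such events will often be non-serious, and non-serious events are not kept after day 70 even when drug-related.

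**Working it through.** The documents do not state the length of the gap, so there is no figure to reproduce. It follows from calendar arithmetic.

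**Inputs**
- Cycle length 42 days; no dose in every third cycle (Synopsis; Operations Manual 6.1).
- All-AE window: through day 70 after the last dose (Sections 3.3 and 7.5; Operations Manual 4.1).
- Visit windows and End of Treatment timing (Operations Manual 2.3).

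**Step 1: dosing gaps.** Counting from the first Arm B dose as day 0, doses fall on days 0, 42, 126, 168, 252 and 294. The gaps are 42, 84, 42, 84 and 42 days. The long gap is 2 × 42 = 84 days, which is 84 − 70 = 14 days longer than the window. With the ±2-day window on one Day 1 visit it is 82–86 days; with both shifted, 80–88. It exceeds 70 throughout.

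**Step 2: days affected.** With the next dose due on after-dose day 84, the exposed days are 71 to 83: 83 − 70 = 13 days. With the 80–88 range this becomes 79 − 70 = 9 to 87 − 70 = 17 days. Day k of the omitted cycle is after-dose day 42 + k − 1, so day 70 is Day 29 and days 71–83 are Days 30–42. That is 13/42 = 31% of the omitted cycle and 13/84 = 15% of the gap.

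**Step 3: visits in the omitted cycle**

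| Contact | Cycle days | After-dose days | Relation to day 70 |
|---|---|---|---|
| Day 15 ± 2 | 13–17 | 54–58 | inside |
| Day 22 + 2 call | 22–24 | 63–65 | inside |
| Day 29 ± 3 | 26–32 | 67–73 | straddles |
| Day 36 + 2 call | 36–38 | 77–79 | beyond |
| Post-cycle assessment | 35–42 | 76–83 | beyond |

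The post-cycle assessment carries both the disease assessment and an AE query. In a dosed cycle it falls on after-dose days 34–41, well inside the window. If the decision to stop is taken on after-dose days 71–84, End of Treatment can be as late as 71 + 7 = 78 to 84 + 7 = 91. The latest case is 91 − 70 = 21 days past the limit, again with an AE query.

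**Step 4: one event, two outcomes.** Take a non-serious AE starting on after-dose day 78.
- A dose is given on day 84: the last dose is on day 84 or later, so the event is reportable, treatment-emergent and in the summary.
- Treatment stops: the earlier dose is the last one, and 78 > 70, so the event is outside the reporting rule, the treatment-emergent definition and the summary.

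**Step 5: dose holds (assumption).** The documents do not say whether the 6-week maximum interruption is added to the planned interval. If it is, the omitted-cycle gap could reach 84 + 42 = 126 days, and the gap between the two Arm A retreatment doses 42 + 42 = 84 days. If it is not, they stay at 84 and 42 days.

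**The case against.** The strongest reply is that little need be lost. Section 3.3 also runs AE collection to study end, and Section 6.1 has investigators monitoring AEs throughout the study. AE queries are scheduled at the omitted-cycle visits, End of Treatment and long-term follow-up, and the AE listing in Section 7.5 has no stated 70-day cut-off. This stands in part: loss at collection is not established, because the texts conflict. It does not rescue the treatment-emergent definition or the disclosure summary, which both carry the 70-day limit explicitly.

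A second reply is that no dose has been shown to be the last while further dosing is planned, so a site would simply keep reporting. That is a reasonable reading, and uneven SAE reporting between sites is a possibility rather than something the text shows. But once treatment stops, the definition and the summary apply in retrospect and exclude the event, even if the site recorded it.

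Third, the visits beyond day 70 are not themselves lost data. An AE that began earlier and is reported there still counts; only onset or worsening after day 70 is affected.

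Fourth, Section 3.3 refers to a schema and Operations Manual 4.1 to a diagram, and neither is reproduced in the text available for this review. They might address the gap. The written rules contain no exception for it.

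Finally, the stakes are modest. There is no control group, no formal safety analysis is planned, and most subjects are expected in Arm A. All of that stands and limits the weight of the point.

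**Conclusion.** The point holds in a limited form. Across each omitted Arm B cycle, non-serious AEs and SAEs judged unrelated that start on after-dose days 71–83 are treatment-emergent and enter the disclosure summary if another dose is given, and are excluded if treatment stops. The 13-day figure assumes on-schedule dosing. The effect is confined to safety listings and the disclosure summary. Its direction is toward missing events in subjects who discontinue; its size cannot be computed, because the documents give no event rates and no sample size.

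Two stronger readings are tempting and not supported:
- A reader might infer that AEs which end treatment in the omitted cycle disappear altogether. They do not: treatment-related SAEs after day 70 are still collected and summarized, and Section 7.3 lists the reason for stopping study drug by subject. That reason is not a full AE record, but it is not nothing.
- A reader might infer that Arm A retreatment has the same built-in gap, or that Arm B gaps run to 126 days. Retreatment is limited to two cycles per period with no planned omission. Both extensions depend on reading the maximum interruption as additional to the planned interval, in a footnote that belongs to the hematologic toxicity table.

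**What to change.** In Sections 3.3 and 7.5 and Operations Manual 4.1, state for Arm B and Arm A Retreatment that:
- all AEs are reported, counted as treatment-emergent and summarized until the later of 70 days after the last dose and the End of Treatment visit;
- omitted cycles and dose holds lie inside the window whether or not a further dose follows;
- collection of treatment-related SAEs only begins after that.

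Reconcile the Section 3.3 sentence on collection to study end with this rule, and check the schema and diagram against it. Section 5.4 uses the same 70-day cut-off for concomitant medication and should be read alongside.

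The end of the window would still depend on when the stop decision is made, but every day on treatment up to that decision would be covered whichever way it goes. For a stop decided by after-dose day 63 (63 + 7 = 70), with End of Treatment held within its window, the 70-day limit still governs and nothing changes.

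The cost is wording in the protocol and Operations Manual. No visits are added, because the AE queries are already scheduled. The downside is slightly more AEs in the summary, including disease-related ones.
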